### **8.11.3 Treatment Period (Visit 4-Visit 6)**

After 5-week run-in treatment, participants who archive  $\geq 75\%$  compliance with the run-in medication and have not met their treatment goals for LDL-C according to their risk levels will be eligible for study entry. The site will perform all procedures for Visit 4 and the participant will be randomized. After the all procedures have been completed, the study drugs will be dispensed and the participants should take the treatment at a consistent time each day to promote compliance.

The following visits will be scheduled every 6 weeks for participants to return to perform the study procedures required as per Section 1.3 – SoA.

### **8.11.4 Discontinued Participants Continuing to be Monitored in the Study**

Participants who discontinue study treatment prior to completion of the treatment period should be encouraged to continue to be followed for all remaining study visits.

### **8.11.5 Poststudy (follow-up visit)**

Participants will be followed-up by phone approximately 14 days after the last dose of study intervention to determine if any AEs have occurred since the last clinic visit.

## **9 STATISTICAL ANALYSIS PLAN**

This section outlines the statistical analysis strategy and procedures for the trial. If, after the trial has begun, but prior to any unblinding, changes are made to the study hypotheses, or the statistical methods related to those hypotheses, then the protocol will be amended (consistent with ICH Guideline E9). Changes to exploratory or other non-confirmatory analyses made after the protocol has been finalized, but prior to unblinding, will be documented in a supplemental SAP (sSAP) and referenced in the Clinical Study Report (CSR) for the trial. Post hoc exploratory analyses will be clearly identified in the CSR.

## 9.1 Statistical Analysis Plan Summary

Key elements of the statistical analysis plan are summarized below; the comprehensive plan is provided in Sections 9.2-9.12.

Study Design Overview	A Phase III, Randomized, Double-blind Clinical Trial to Study the Efficacy and Safety of MK-0653C in Chinese participants with Hypercholesterolemia
Treatment Assignment	A double-blind/masking technique will be used. After the run-in period, 180 participants will be randomized in a ratio of 1:1 into the arms of MK-0653C 10/10 mg and atorvastatin 20 mg in Cohort A and 270 participants will be randomized in a ratio of 1:1 into the arms of MK-0653C 10/20 mg and atorvastatin 40 mg in Cohort B. Randomization will be stratified by disease risk category (low, moderate, high, very high) as defined in Section 4.1.
Analysis Populations	Efficacy: Full Analysis Set (FAS) Safety: All Participants as Treated (APaT)
Primary Endpoint	Percent change from baseline in LDL-C at Week 12
Secondary Endpoints	1. Percentage of participants with adverse events. 2. Change from baseline in laboratory parameters and vital signs at each visit 3. Percentage of participants discontinued from study medication
Statistical Methods for Key Efficacy Analyses	The primary hypothesis for each cohort will be evaluated by comparing MK-0653C to atorvastatin on the percent change from baseline in LDL-C using a constrained longitudinal data analysis (cLDA) model.
Statistical Methods for Key Safety Analyses	Counts and percentages of AEs will be provided. P-values and confidence intervals for the incidence of AEs of clinical interest will be estimated using the Miettinen and Nurminen method [Miettinen, Olli and Nurminen, Markku 1985].
Interim Analyses	No interim analyses are planned for this trial.
Multiplicity	The Type-I error rate over the multiple treatment comparisons will be controlled by the Hochberg testing procedure.
Sample Size and Power	A total of approximately 450 participants (180 in Cohort A, 270 in Cohort B) will be randomized. The sample in Cohort A has 93% power to demonstrate the superiority of MK-0653C 10/10 mg over atorvastatin 20 mg at a one-sided 2.5% alpha-level. Similarly, the sample in Cohort B has 95% power to demonstrate the superiority of MK-0653C 10/20 mg over atorvastatin 40 mg at a one-sided 2.5% alpha-level. The overall power to succeed on at least one hypothesis is 99% at a 2.5% alpha-level with 88% power to succeed for both hypotheses.

## 9.2 Responsibility for Analyses/In-house Blinding

The statistical analysis of the data obtained from this trial will be the responsibility of the Clinical Biostatistics department of the Sponsor.

This trial will be conducted as a double-blind trial under in-house blinding procedures. The official, final database will not be unblinded until medical/scientific review has been performed, protocol deviations have been identified, and data have been declared final and complete.

The Clinical Biostatistics department will generate the randomized allocation schedule(s) for study treatment assignment. Randomization will be implemented in an interactive voice response system/integrated web response system (IVRS/IWRS).

### **9.3 Hypotheses/Estimation**

Objectives and hypotheses of the study are stated in Section 3.

### **9.4 Analysis Endpoints**

Efficacy and safety endpoints that will be evaluated for between-treatment differences are listed below.

#### **9.4.1 Efficacy Endpoints**

1. Percent change from baseline in LDL-C at Week12.
2. Percentage of participants meeting the LDL-C treatment goal (see [Table 13](#) in Appendix 7) at Week 12.
3. Percent change from baseline in LDL-C at Week 6.
4. Percent change from baseline in total cholesterol (TC), HDL-C, non-HDL-C, triglyceride (TG), Apo protein (Apo) B at Weeks 6 and 12.

#### **9.4.2 Safety Endpoints**

1. Percentage of participants with adverse events.
2. Change from baseline in laboratory parameters and vital signs at each visit.
3. Percentage of participants discontinued from study medication.

### **9.5 Analysis Populations**

#### **9.5.1 Efficacy Analysis Populations**

The Full Analysis Set (FAS) population will serve as the primary population for the analysis of efficacy data in this trial. The FAS population for any given endpoint consists of all randomized participants who took at least one dose of study treatment, and have at least one observation of the respective endpoint (baseline or post-baseline) during the treatment period.

Participants will be included in the treatment group to which they are randomized for the analysis of efficacy data using the FAS population. Details on the approach to handling missing data are provided in Section 9.6 Statistical Methods.

## 9.5.2 Safety Analysis Populations

Analyses of safety data will be performed in the All Participants as Treated (APaT) population, consisting of all randomized participants who received at least one dose of study treatment. Participants will be included in the treatment group corresponding to the study treatment they actually received for the analysis of safety data using the APaT population. This will be the treatment group to which they are randomized for all participants except for those who take incorrect study treatment for the entire treatment period. Such participants will be included in the treatment group corresponding to the study treatment actually received. At least one laboratory measurement or vital sign obtained subsequent to at least one dose of study treatment is required for inclusion in the analysis of each specific parameter. To assess change from baseline, a baseline measurement is also required.

Details on the approach to handling missing data for safety analyses are provided in Section 9.6 Statistical Methods.

## 9.6 Statistical Methods

Statistical testing and inference for safety analyses are described in Section 9.6.2. Nominal p-values may be computed for other efficacy analyses, but should be interpreted with caution due to potential issues of multiplicity, sample size, etc. Unless otherwise stated, all statistical tests will be conducted at  $\alpha=0.05$  (2-sided) level.

### 9.6.1 Statistical Methods for Efficacy Analyses

This section describes the statistical methods that address the primary and secondary objectives.

The study's estimand is a hypothetical estimand that seeks to estimate efficacy as if all participants were to take study medication for 12 weeks.

The estimand consists of the following elements:

- Target population: Participants with hypercholesterolemia (age 18 to 80 years, inclusive), consistent with the study's inclusion/exclusion criteria.
- Variable: Percent change from baseline in LDL-C at Week 12.
- Intercurrent event: Data obtained after discontinuation of treatment are not relevant to this estimand.
- Population level-summary: Difference in variable means comparing randomized treatments (within each cohort).

Analyses will thus exclude measurements collected more than 5 days after the last dose of study treatment.

For the analyses of percent change from baseline in LDL-C at Week 12 in both cohorts, a constrained longitudinal data analysis (cLDA) method proposed by Liang and Zeger will be used [Liang, Kung-Yee and Zeger, Scott L. 2000]. Within each baseline disease risk category (i.e., stratum), this model assumes a common mean across treatment groups at baseline and a different mean for each treatment at each of the post-baseline time points. In this model, the response vector consists of baseline and the values (percent change) observed at each post-baseline time point. Time is treated as a categorical variable so that no restriction is imposed on the trajectory of the means over time. The analysis model will adjust for time and the interaction of time by treatment, and time by baseline disease risk category given in Section 4.1. The treatment difference in terms of mean change from baseline to Week 12 will be estimated and tested from this model. An unstructured covariance matrix will be used to model the correlation among repeated measurements.

Although the baseline measurement is included in the response vector, it is independent of treatment, and hence, the stratum-specific baseline means are constrained to be the same for different treatment groups. Of note, in the event that there are no missing data, the estimated treatment difference from the above cLDA model will be identical to that from a traditional longitudinal ANCOVA model which uses the baseline value as a covariate. However, unlike longitudinal ANCOVA, the cLDA model accounts for variability in the baseline values, thus providing more accurate standard errors and confidence intervals for individual treatment effects. Moreover, this model allows the inclusion of participants who are missing either the baseline or post-baseline measurements, thereby increasing efficiency. Details of the model specification, assumptions, and SAS implementation codes will be provided in the sSAP.

The cLDA method assumes that the mechanism for missing data is missing at random (MAR). Sensitivity analyses will be performed to assess the robustness of the conclusions from the cLDA analyses to departures from MAR. The details will be described in sSAP.

The percentage of participants reaching the LDL-C goals will be analyzed via a logistic regression model with LDL-C goal achievement rate as response variable and treatment and baseline disease risk category given in Section 4.1 as explanatory variables. Odds ratio estimate derived from the logistic regression model and 95% CI will be used to quantify the treatment effect. Imputation of missing data will be based on the marginal univariate normal distributions with means equal to the predicted values and variances equal to the squared standard errors for the predicted values from the cLDA model. Ten sets of imputations of each missing value will be constructed from the cLDA model. Odds ratio estimate derived from the logistic regression model and 95% confidence interval will be used to quantify the treatment effect. Other exploratory endpoints will be evaluated using the same cLDA model, but TG will be transformed by the natural logarithm on account of the non-normality of this endpoint. Geometric mean percent changes from baseline in TG will be calculated based on back-transformation via exponentiation of the model-based LS means and expressed as (geometric mean – 1) multiplied by 100. The treatment differences in geometric mean percent changes from baseline will be calculated based on the difference in the back transformed model-based LS means and 95% confidence intervals (CIs) for the differences will be calculated using the delta method [Wong, P., et al 1999]. Key efficacy analysis is summarized in [Table 6](#).

Table 6 Analysis Strategy for Key Efficacy Variables

Endpoint/Variable	Statistical Method	Analysis Population	Missing Data Approach
Primary Hypotheses			
Percent change from baseline in LDL-C at Week 12	cLDA †	FAS	Model-based
† Constrained LDA model with terms for treatment, time, the interaction of time by treatment and time by baseline disease risk category.			

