### 1.3 Schedule of Activities (SoA)

Study Period	Screening	Active run-in period (5 weeks)		Treatment (12 weeks)			Follow-up (14 days post last dose)	Notes
Visit Number/Title	Visit 1/ Screening	Visit 2	Visit 3	Visit 4/ baseline	Visit 5	Visit 6/ Discontinuation	Phone call	
Scheduled Hour, Day, Week, etc., and Window:	Week -7/-6	Week -5 (±7 days)	Week -1 (+3 days)	Week 0 (±3 days)	Week 6 (±7 days)	Week 12 (±7 days)	±3 days	The dates of Visit 3 and Visit 4 will be decided based on the date of Visit 2, while the dates of Visit 5 & Visit 6 will be decided based on the date of Visit 4.
Administrative Procedures								
Informed Consent	X							
Inclusion/Exclusion Criteria	X			X				
Participant Identification Card	X							The card will be updated once randomized.
Medical History	X							
Prior/Concomitant Medication Review	X	X	X	X	X	X		
Assignment of Screening Number	X							
LDL-C treatment target evaluation based on Cardiac Risk assessment	X							Based on Chinese Guidelines on Prevention and Treatment of Dyslipidemia in Adults (2016 Edition).
Monitor Dietary/Exercise Compliance	X	X	X	X	X	X		
Monitor Medication Compliance			X	X	X	X		
Assignment of Treatment/Randomization number				X				

Study Period	Screening	Active run-in period (5 weeks)		Treatment (12 weeks)			Follow-up (14 days post last dose)	Notes
Visit Number/Title	Visit 1/ Screening	Visit 2	Visit 3	Visit 4/ baseline	Visit 5	Visit 6/ Discontinuation	Phone call	
Scheduled Hour, Day, Week, etc., and Window:	Week -7/-6	Week -5 (±7 days)	Week -1 (+3 days)	Week 0 (±3 days)	Week 6 (±7 days)	Week 12 (±7 days)	±3 days	The dates of Visit 3 and Visit 4 will be decided based on the date of Visit 2, while the dates of Visit 5 & Visit 6 will be decided based on the date of Visit 4.
Run-in atorvastatin administration/dispensing		X						
MK-0653C/ Atorvastatin + matching placebo administration/dispensing				X	X			
Efficacy Procedures								
Lipid Panel A	X		X	X	X	X		LDL-C, total cholesterol (TC), HDL-C, non-HDL-C, and Triglyceride (TG). Blood sample should be drawn after at least 10-hour fasting. Otherwise the visit need to be rescheduled. Result of local lab within 4 weeks prior to Visit 1 can be used as reference for participant screening.
Apo protein (Apo) B				X	X	X		Blood sample should be drawn after at least 10-hour fasting. Otherwise the visit needs to be rescheduled.
Safety Procedures								
Full Physical Examination including height and weight	X			X		X		

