## 9.9 Sample Size and Power Calculations

A total of approximately 450 participants (180 in Cohort A, 270 in Cohort B) will be randomized. The power computation has been performed conservatively based on the number of participants expected to have LDL-C data at Week 12. Assuming a drop-out rate of 10%, 162 participants (81 per arm) in Cohort A and 242 participants (121 per arm) in Cohort B will be available for the power calculation. The sample in Cohort A has a 93% power to demonstrate the superiority of MK-0653C 10/10 mg over atorvastatin 20 mg at a one-sided 2.5% alpha-level. The half-width of the 95% confidence interval for the between-treatment difference is expected to be 7.0%. Similarly, the sample in Cohort B has a 95% power to demonstrate the superiority of MK-0653C 10/20 mg over atorvastatin 40 mg at a one-sided 2.5% alpha-level. The half-width of the 95% confidence interval for the between-treatment difference is expected to be 5.7%. The overall power to success on at least one hypothesis is 99% at a 2.5% alpha-level with 88% power to succeed for both hypotheses. If only one hypothesis is successful according to Hochberg procedure, the sample in Cohort A will result in a power of 88% and the sample in Cohort B will result in a power of 91% at 1.25% alpha-level. The power and sample sizes are based on the following assumptions: the treatment difference in percent changes from baseline in LDL-C at Week 12 are 12.3% and 10.5%, and unconditional standard deviations are 22% and 23% for Cohorts A and B, respectively, according to P162 results from the ANCOVA model.

The safety power table displays a range of AE rates and the possible difference that can be detected with the sample size of the study at 90% and 80% power is shown in [Table 8](#). All calculations are based on 2-sided  $\alpha=0.05$  significance level.

Table 8 Safety Power Calculation

AE rate in Atorvastatin 20 mg or 40 mg Group	Percentage Point Difference in Cohort A (MK-0653C 10/10 mg- Atorvastatin 20 mg) Power of 80% (90%)	Percentage Point Difference in Cohort B (MK-0653C 10/20 mg- Atorvastatin 40 mg) Power of 80% (90%)
1%	10.3 (12.2)	8.2 (10.0)
2%	11.4 (13.5)	9.2 (11.1)
3%	12.3 (14.6)	9.9 (11.9)
AE = adverse event		

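### The exploratory LDL-C goal-attainment model leaves out baseline LDL-C, a prognostic value already collected at Visit 4; the planned analysis is valid but gives up some power

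*Combined protocol and SAP*

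**What the plan says.** Section 4.2.1.1 makes the proportion at LDL-C goal an exploratory endpoint, and Section 9.6 treats p-values outside the primary tests as nominal. The goals, in Table 13 of Appendix 7, are below 130, 100 and 70 mg/dL for low/medium, high and very high risk.

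Section 9.6.1 specifies a logistic model with "treatment and baseline disease risk category given in Section 4.1 as explanatory variables". The odds ratio and its 95% CI are to quantify the effect. Missing values are drawn as normal variates, the parameters being "means equal to the predicted values and variances equal to the squared standard errors for the predicted values from the cLDA model". The number of draws is fixed as well: "Ten sets of imputations of each missing value will be constructed from the cLDA model"; no rule for combining the ten sets is stated.

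The primary model in the same section does use baseline LDL-C. It sits in the cLDA response vector, and with complete data the estimated difference is said to match "a traditional longitudinal ANCOVA model which uses the baseline value as a covariate". The Schedule of Activities draws Lipid Panel A at "Visit 4/ baseline". Section 9 allows exploratory analyses to be changed before unblinding if this is documented in the supplemental SAP.

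**The concern.** Whether a participant gets below a fixed cut-off depends heavily on where that participant starts. Risk category captures part of this, because it sets both the goal and the entry limits, but a wide spread of LDL-C remains inside each category. Leaving a strong predictor out of a logistic model pulls the treatment odds ratio towards 1 relative to the baseline-conditional one and lowers power, although the value is collected anyway and the primary model relies on it.

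The imputation wording raises a smaller question. A standard error for a predicted value can mean that of a fitted mean or that of an individual prediction. For a threshold endpoint the spread of the imputed values decides how many fall on each side of the cut-off, so the two meanings can give different odds ratios.

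At stake is the precision and clarity of one exploratory result.

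**Working it through.** **Plan's own figures.** No power, goal rate or odds ratio is given for goal attainment. The Section 9.9 inputs used below are differences of 12.3 and 10.5 points, "unconditional standard deviations are 22% and 23% for Cohorts A and B", and 81 and 121 evaluable per arm. They reproduce the stated primary power, Φ(d/(SD√(2/n)) − 1.96):

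- Cohort A: 12.3/(22√(2/81)) = 3.56, so power is 94.5% (93% stated).
- Cohort B: 10.5/(23√(2/121)) = 3.55, so power is 94.4% (95% stated).

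**How prognostic baseline is.** Inclusion criterion 11 admits 70–160 mg/dL for very high risk and 100–160 for high risk at Visit 3. The reduction needed therefore runs from about 0 to 1 − 70/160 = 56%, and from about 0 to 1 − 100/160 = 37.5%. As an illustration, take two very-high-risk control participants, a mean change of −6% (Section 2.2.1 expects 6–7% from doubling a statin dose), SD 22 and no correlation between baseline and change:

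- Baseline 75 mg/dL needs 1 − 70/75 = 6.7%: Φ((−6.7 + 6)/22) = 0.49.
- Baseline 140 mg/dL needs 50%: Φ((−50 + 6)/22) = 0.02.

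A negative correlation narrows this gap, because higher baselines then fall further.

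**Power with and without baseline.** Simulation: 90 or 135 randomised per arm, two-sided 0.05 Wald test, 144 scenarios of 1,500 trials. Assumed because undocumented: three risk mixes; lognormal Visit 3 LDL-C (log SD 0.22) truncated to the entry limits; visit-to-visit SD 8%; control change −6% or −10%. Gain in percentage points from adding Visit 4 LDL-C:

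| Correlation of log baseline with percent change | Cohort A | Cohort B |
|---|---|---|
| 0 | 5.9–8.9 | 5.4–8.5 |
| −0.2 | 1.9–4.6 | 1.5–4.3 |
| −0.3 | 1.1–2.7 | 0.4–2.3 |
| −0.4 | about 0–1.7 | about 0–1.7 |

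With log SD 0.15 or 0.30 the extremes are −0.7 and 9.6. A separate simulation at 81 and 121 per arm, with other assumed baselines and control changes, gave 5–7 points at 0, 0–1 at −0.3 and about 0 at −0.5. It gave 7–8 at +0.1 and 10–13 at +0.2. A third gave 7.6–7.8 at 0, about 3 at −0.2, 1–2 at −0.3 and 0.5–1.5 at −0.4.

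**Why power rises although the standard error does too.** At correlation 0, using mid-range odds ratios:

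- Cohort A without baseline: ln(2.235)/0.332 = 2.42, power Φ(2.42 − 1.96) = 0.68. With baseline: ln(2.605)/0.370 = 2.59, power 0.73 to 0.74.
- Cohort B without baseline: ln(1.915)/0.268 = 2.42, power 0.68. With baseline: ln(2.16)/0.294 = 2.62, power about 0.75.

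The log odds ratio grows more than its standard error, which rises 9–12% at 0, 3–4% at −0.3 and 1–2% at −0.4. On the standardised difference in proportions the empirical SD falls 7–10%, 1–3% and 0–2% respectively.

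**Validity.** Under the null (4 × 4,000 trials) rejection was 4.8–5.6% without baseline and 4.7–6.0% with it; the median odds ratio was 0.99–1.01.

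**Imputation.** The SE of an arm mean is about 22/√81 = 2.4 points (A) or 23/√121 = 2.1 (B), and 3–4 points for a fitted value in the simulations. An individual prediction has an SD of about 18–22. At 10% missing:

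- Fitted-mean reading: the odds ratio rose 3.6–5.7% (A) and 2.6–4.0% (B) in one simulation, and mostly 3–7% in another (extremes 2–17%).
- Individual-prediction reading: the odds ratio stayed within about 1% of the full-data value.

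In Cohort A, 3–7% is ln(1.03) to ln(1.07) = 0.030–0.068, or about 0.1–0.2 of the standard error of 0.332.

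**The case against.** The strongest reply is that the plan contains no error here. An odds ratio adjusted for the stratification factor is a legitimate choice, the endpoint is exploratory, and no power was promised for it. The loss may be close to nil, because measurement error in baseline enters percent change with the opposite sign and so makes a negative correlation likely. All of this stands and limits the size of the point. It does not show any harm from adding the covariate, beyond a change in what the odds ratio means.

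Baseline LDL-C also already informs the imputation through the cLDA. That is true, but it helps only the missing values and not the observed majority.

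The simulations use three risk groups where the plan stratifies by four. Low and moderate risk share the same goal and entry limit, so the effect is probably small, but the planned model was not simulated exactly.

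Four stronger readings are tempting and not supported:

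- *The analysis is biased or invalid.* The null results show otherwise.
- *The plan loses 5 to 9 points of power.* That needs a correlation near zero, which the documents neither state nor make likely.
- *The imputation inflates the odds ratio.* Section 9.6.1 describes draws for individual missing values and speaks of LS means when it means means, so the individual-prediction reading is the more natural one. Details of the cLDA are deferred to a supplemental SAP that is not available here.
- *Missingness will exceed the 10% of Section 9.9.* "Analyses will thus exclude measurements collected more than 5 days after the last dose of study treatment" does mean that someone who stops early may be imputed despite attending Week 12. Section 9.9 counts participants expected to have Week 12 data, and does not say whether its 10% already covers such cases.

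**Conclusion.** The point holds as a minor improvement. The goal-attainment model omits a prognostic covariate that the trial already collects; the cost is power only. The power ranges are illustrative: they rest on assumed baseline distributions, risk mix and control response, and above all on the correlation between baseline and percent change. At −0.3 to −0.4 the cost is about 0–3 points, and at zero about 5–9. A positive correlation would raise it further, but is less plausible.

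The imputation wording is a secondary matter of clarity. Only if it were implemented as the SE of a fitted mean would the odds ratio move away from 1, by roughly 3–7% at 10% missing.

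**What to change.** In the supplemental SAP, before unblinding:

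1. Add Visit 4 LDL-C as a continuous covariate to the goal-attainment logistic model, and label the odds ratio as conditional on baseline LDL-C and risk category.
2. Report standardised proportions at goal by arm and their difference with a 95% CI. This is the scale on which the interval can narrow; the interval for the log odds ratio will not.
3. State that each missing Week 12 value is drawn with residual (conditional) variance plus the squared standard error of prediction, and that the ten sets are combined by Rubin's rules.

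The cost is a few sentences and a few lines of code, with no new data. The drawback is that the odds ratio becomes numerically larger (at zero correlation, Cohort A moves from 2.16–2.31 to 2.52–2.69), carries a somewhat larger standard error, and cannot be compared directly with one adjusted for risk category only. If that comparison matters, the currently planned odds ratio can be kept alongside.
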